 - o If surgery was >120 days after the inclusion visit, but subjective assessment was not always probably or certainly malignant (including borderline) at every visit: classify as *uncertain (U1)*

- B. The tumor spontaneously resolved at any point during follow-up: classify as *benign*

- C. The patient did not receive surgery, the tumor did not resolve, and the last follow-up visit was ≥ 10 months after the inclusion visit:

- If subjective assessment was consistently labeled as probably or certainly benign during the first 14 months of follow-up (specific definition: subjective assessment was benign at the earliest visit after ≥ 10 months of follow-up, and subjective assessment was benign at all visits up to 14 months of follow-up): classify as *benign (B2)*
- If subjective assessment was consistently labeled as probably or certainly malignant (including borderline) during first 14 months of follow-up (specific definition: subjective assessment was borderline/malignant at the earliest visit after ≥ 10 months of follow-up, and subjective assessment was borderline/malignant at all visits up to 14 months of follow-up): classify as *malignant (M3)*
- Else, subjective assessment was inconsistent/uncertain during the first 14 months of follow-up: classify as *uncertain (U2)*

D. Other cases: classify as *uncertain*

- Patients that received follow-up of less than 10 months, without receiving surgery or experiencing spontaneous resolution of the tumor. Reasons for such short follow-up can be death, withdrawal from the study, or being lost to follow-up. (U3)
- Patients for which we did not have information after the inclusion visit. Reasons for such short follow-up can be death, withdrawal from the study, or being lost to follow-up. (U4)

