Multiple imputation will be performed to deal with missing values for CA125 and outcome. Imputations will be created using the method of fully conditional specification with the mice package in R. We will generate 100 imputations, leading to 100 completed datasets. To estimate the missing values for CA125, we will use predictive mean matching regression using the outcome, variables that are probably related to either the level of CA125 itself, or to the unavailability of CA125 (i.e. a binary indicator indicating for each patient whether CA125 was missing). As the distribution of serum CA125 was heavily skewed, the log-log transformation of CA125 will be used (i.e., $\log(\log(\text{CA125} + 1))$). In the imputation model, the following variables will be used: Presumed endometrioma, level of certainty at subjective assessment at inclusion (6 groups: certainly benign, probably benign, benign but uncertain, malignant but uncertain, probably malignant, certainly malignant), patient age, type of center (oncological versus non-oncological center), lesion largest diameter, proportion of solid tissue (maximum diameter solid component divided by maximum diameter of lesion), number of locules (1, 2-10, >10, other), number of papillations, presence of shadows, presence of ascites, presence of metastases, bilaterality, pelvic pain, personal history of ovarian cancer, papillary height, papillary flow, color score, echogenicity of cyst fluid, and outcome (benign, borderline, stage I primary invasive, stage II-IV primary invasive, secondary metastatic). Descriptive characteristics of the tumor were based on the inclusion scan. Uncertain outcomes (cf above) will be considered missing, and hence the outcome will be imputed).

Note that some patients are classified as having a malignant tumor based on clinical and ultrasound information during follow-up (cf category M3 above). For these patients, we do not have a classification into one of the malignancy subtypes. The multiple imputation procedure will therefore treat the outcome as missing such that it will be imputed. The imputed outcomes will be evaluated, and the most commonly imputed malignant type will be used as the outcome in the analysis.

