1.5.2 How to deal with patients with uncertain outcome in the analysis

The outcome is a part of the imputation procedure described above, hence we have imputed values. The primary analysis is based on the multiply imputed values for CA125 and the outcome (cf de Groot, 2011).

As described below, we will also perform a sensitivity analysis after omitting patients with an uncertain outcome, and a sensitivity analysis after imputation of the outcome for patients where the outcome was labelled as uncertain, or was derived using information on subjective assessment (groups B2, M2, M3, U1, U2, U3, U4).

Note that models including CA125 (RMI and ADNEX with CA125) will always be analysed using imputed data for CA125, even when patients with uncertain outcome are omitted. Hence, only when evaluating models without CA125 based on patients for which the outcome is not labelled as uncertain, we do not have to use multiply imputed data.

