1.5.6. Additional analysis for ADNEX

We will further analyse the ADNEX predictions in terms of discrimination and calibration. First, c-statistics between each pair of outcome categories will be computed using the conditional method (Van Calster, 2012). Only pooled results will be shown (i.e. no meta-analysis) because some outcome categories will have few events in several centers. For imputed data, logit(AUC) will be computed for each imputation, and combined using Rubin Rules.

Second, multinomial logistic calibration curves will be constructed (Van Hoorde 2014). For imputed data, curves will be derived per imputed dataset, and averaged.

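### Giving M3 patients the most commonly imputed malignant type is single modal imputation; it shifts the subtype mix and drops one variance component in the ADNEX subtype results

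*SAP*

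**What the plan says.** All references are to the model-performance part of the SAP (28 May 2019).

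- **Who is M3 (section 1.3, outcome rule C).** No surgery, no resolution, last visit at 10 months or later, and a consistent malignant or borderline judgement: "subjective assessment was borderline/malignant at all visits up to 14 months of follow-up". These patients are classed as malignant.
- **Why a subtype is needed (section 1.5.1).** "For these patients, we do not have a classification into one of the malignancy subtypes". The outcome is therefore set to missing and imputed. The outcome variable has five categories, one of which is benign.
- **What is done with the draws (section 1.5.1).** "We will generate 100 imputations, leading to 100 completed datasets". For M3, however, "the most commonly imputed malignant type will be used as the outcome in the analysis".
- **How other missing outcomes are treated (sections 1.5.1 and 1.5.2).** For U1 to U4, "Uncertain outcomes (cf above) will be considered missing, and hence the outcome will be imputed", with no reduction to a mode. "The primary analysis is based on the multiply imputed values for CA125 and the outcome".
- **Where the subtype is used (section 1.5.6).** Pairwise c-statistics between outcome categories: "For imputed data, logit(AUC) will be computed for each imputation, and combined using Rubin Rules". Multinomial calibration curves are derived in each dataset and averaged.

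**The concern.** Replacing many draws by their mode has two known consequences. The distribution of the filled-in values is pulled toward the commonest category. The values also no longer differ between datasets, so Rubin's rules treat a guessed subtype as if it had been observed. Section 1.5.6 needs both features to be right: it compares subtypes with one another, and it pools on the premise that unknown outcomes vary across the 100 datasets.

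There is a second, smaller route. CA125 is imputed with the outcome as a predictor. The SAP states no malignant-only restriction on the M3 draws, so an M3 patient without CA125 may have it imputed in a dataset where the outcome was drawn as benign. The patient is then analysed as malignant with that CA125 value. This can reach the results of RMI and of ADNEX with CA125.

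The planned checks do not cover the point. The sensitivity analysis that re-imputes M3 (sections 1.5.2 and 1.5.8) reports only the overall benign-versus-malignant c-statistic and overall calibration curves.

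**Working it through.** The plan gives no figure to reproduce: it states no M3 count, no number of malignancies and no subtype probabilities. What follows is an illustration on assumed inputs.

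**Assumed inputs**
- Mean subtype probabilities in M3 (borderline / stage I / stage II-IV / metastatic): 40/20/30/10%.
- Borderline share among all other malignancies: 25%.
- k M3 patients among N malignancies: k = 5 or 20 with N = 500, and an extreme case of k = 50 with N = 200.
- Individual probabilities follow a Dirichlet distribution around the mean, with concentration 2 (patients well separated) or 20 (patients similar).
- From the SAP: 100 imputations.

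**Step 1. Subtype mix within M3.** Retaining every draw reproduces 40/20/30/10% on average. A group mode gives 100/0/0/0% when borderline is the mode. For the per-patient mode I simulated 100,000 patients, each with 100 draws:

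| Patients | Borderline | Stage I | Stage II-IV | Metastatic |
|---|---|---|---|---|
| Well separated | 43.9% | 18.1% | 30.0% | 8.0% |
| Similar | 64.5% | 7.8% | 26.7% | 1.0% |

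With k = 20 and similar patients, expected counts of 8/4/6/2 become 20 × (0.645, 0.078, 0.267, 0.010) = 12.9/1.6/5.3/0.2. The less common types lose most in relative terms.

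**Step 2. Borderline share of all malignancies** = [0.25 × (N − k) + k × borderline share within M3] / N, similar patients:

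| N, k | All draws kept | Per-patient mode | Group mode |
|---|---|---|---|
| 500, 5 | (123.75 + 2)/500 = 25.2% | (123.75 + 3.2)/500 = 25.4% | (123.75 + 5)/500 = 25.8% |
| 500, 20 | (120 + 8)/500 = 25.6% | (120 + 12.9)/500 = 26.6% | (120 + 20)/500 = 28.0% |
| 200, 50 | (37.5 + 20)/200 = 28.8% | (37.5 + 32.2)/200 = 34.9% | (37.5 + 50)/200 = 43.8% |

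**Step 3. Lost variance.** If all M3 patients share the same probabilities, the between-imputation SD of the borderline count is √(k × 0.4 × 0.6): 1.10 for k = 5 and 2.19 for k = 20. Under a mode it is 0. For the standard error of the share s, let W = s(1 − s)/N and B = k × E[p(1 − p)]/N². For similar patients E[p(1 − p)] = 0.24 × 20/21 = 0.2286. The ratio without to with the M3 component is √{W / (W + 1.01 B)}, where 1.01 = 1 + 1/100:

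- N = 500, k = 5: 0.994
- N = 500, k = 20: W = 0.256 × 0.744/500 = 0.000381 and B = 20 × 0.2286/250,000 = 0.0000183, giving 0.977
- N = 200, k = 50: 0.883

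The borderline share stands in for the section 1.5.6 outputs. It is not itself one of them.

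**Step 4. Binary label.** M3 contributes k malignant cases to every dataset under every option, so the number of malignancies is identical.

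**The case against.** A reader might infer that every M3 patient receives the same subtype and that imputation uncertainty disappears from the ADNEX results as a whole. The documents do not support this.

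- Imputation works patient by patient, and the model contains many patient-level features (ascites, metastases, papillations, solid proportion, colour score). A per-patient mode is at least as natural a reading, and with well-separated patients the shift is mild.
- U1 to U4 outcomes and missing CA125 still vary over the 100 datasets. Section 1.5.1 names U3 and U4 as the largest uncertain groups. Only the M3 subtype component is lost.
- ADNEX benign-versus-malignant discrimination, calibration and net benefit do not use the subtype label.
- Scarcity of a subtype within centres is not the relevant denominator, because section 1.5.6 shows pooled results for that very reason.
- No interval is specified for the multinomial calibration curves, so over-narrow intervals can be argued only for the pairwise c-statistics.
- M3 may be small. The protocol keeps cysts with malignant features out of conservative management, and M3 requires at least 10 months without surgery. The CA125 route needs M3 patients who also lack CA125, and that number is not given.

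All of this stands and limits the size of the point. It does not remove it: the rule is still deterministic on either reading, it is still at odds with the pooling in section 1.5.6, and no planned analysis tests its effect on the subtype results.

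**Conclusion.** The point holds in a narrow form, as a low-cost improvement. The modal rule is single imputation for the M3 subtype, it favours the modal type, and it carries no between-imputation variance into results pooled by Rubin's rules. The direct effect is limited to the pairwise c-statistics and multinomial calibration of section 1.5.6. An indirect effect through CA125 on RMI and ADNEX with CA125 is possible and probably slight.

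The size cannot be settled from the documents. Under the assumed inputs with 500 malignancies and 5 to 20 M3 patients, the borderline share moves by about 0.2 to 2.4 percentage points and the standard error falls by about 0.6 to 2.3%. With 50 M3 among 200 malignancies, the shift is about 6 to 15 points and the standard error falls by about 12%. These figures are for similar patients, where the per-patient mode distorts more. A rare subtype could be affected more than the borderline share suggests.

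**What to change.** Replace the modal rule in section 1.5.1 as follows.

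1. Within each of the 100 imputation chains, draw the M3 outcome from the imputation model restricted to the four malignant categories, with probabilities rescaled to sum to one.
2. Impute missing CA125 for these patients given that malignant draw.
3. Keep the dataset-specific subtype in the section 1.5.6 analyses, and pool or average as already planned there.
4. Report the number of M3 patients.

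The separate sensitivity analysis that treats the M3 outcome as fully unknown can stay as it is. If the sponsor prefers to keep a mode, the SAP should say whether it is taken per patient or per group, and should add a sensitivity analysis that reports the section 1.5.6 subtype results with the draws retained.

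The cost is a constraint in the planned imputation code and a rerun. No new data are needed.

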1.5.2 How to deal with patients with uncertain outcome in the analysis

The outcome is a part of the imputation procedure described above, hence we have imputed values. The primary analysis is based on the multiply imputed values for CA125 and the outcome (cf de Groot, 2011).

As described below, we will also perform a sensitivity analysis after omitting patients with an uncertain outcome, and a sensitivity analysis after imputation of the outcome for patients where the outcome was labelled as uncertain, or was derived using information on subjective assessment (groups B2, M2, M3, U1, U2, U3, U4).

Note that models including CA125 (RMI and ADNEX with CA125) will always be analysed using imputed data for CA125, even when patients with uncertain outcome are omitted. Hence, only when evaluating models without CA125 based on patients for which the outcome is not labelled as uncertain, we do not have to use multiply imputed data.

1.5.3 Discrimination between benign and malignant tumors

We will calculate the c-statistic (i.e. AUC) per center, and calculate an overall AUC using random effects meta-analysis on the logit of the center-specific AUCs. In case multiple imputed data are used (e.g. models that include CA125, or when multiply imputed outcome are used), the $\text{logit}(AUC)$ is calculated for each center and herein for each imputed dataset. The latter estimates will then be combined using Rubin's rules and the resulting estimates will be used in a random-effects model to get a final estimate of the AUC.

Sensitivity and specificity will be calculated at the following cut-offs (for models that give predicted risks): 1%, 3%, 5%, 10%, 15%, 20%, 25%, 30%, 40%, and 50%. For the non-imputed data, a bivariate random-effects model will be used to calculate an overall result that takes the clustering by center into account. For imputed data, center-specific sensitivity and specificity as well as their variance (i.e. standard error squared) will be computed, and combined using Rubin's Rules to obtain a final center-specific estimate. These will be used in a bivariate random-effects model to come to a final estimate.

For RMI, we will use cut-offs of 25, 100, 200, and 250. For the Simple Rules classification, we will combine the inconclusive cases with the cases classified as malignant, i.e. inconclusive cases will be classified as malignant.

Because risk models and RMI are on a different scale, it is difficult to directly compare sensitivity or specificity. Therefore, we also calculate the sensitivity when fixing the specificity at 90%, and the specificity when fixing the sensitivity at 90%.

For subjective assessment, we will quantify the overall sensitivity and specificity using a bivariate random-effects model.

For Simple Rules, we will report the percentage of inconclusive cases, and specificity and sensitivity when inconclusives are classified as malignant. This will be done using meta-analysis techniques.

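### The pooling of imputed sensitivity and specificity names neither a scale nor a rule for centres at 0% or 100%; neither direct reading copes with a centre at 100%

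*SAP*

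**What the plan says.** All references are to the SAP's second part, on model performance.

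- **Imputed data, section 1.5.3.** The plan states that "center-specific sensitivity and specificity as well as their variance (i.e. standard error squared) will be computed". The results are "combined using Rubin's Rules to obtain a final center-specific estimate", and then: "These will be used in a bivariate random-effects model to come to a final estimate".
- **Non-imputed data, same paragraph.** "a bivariate random-effects model will be used to calculate an overall result that takes the clustering by center into account". No centre-level variance step is described.
- **AUC, same section.** Here a scale is given: the overall value is obtained "using random effects meta-analysis on the logit of the center-specific AUCs".
- **Cut-offs.** For models that give predicted risks they are "1%, 3%, 5%, 10%, 15%, 20%, 25%, 30%, 40%, and 50" per cent.
- **Which path is primary.** Section 1.5.2 makes the imputed analysis primary, and models with CA125 always use imputed data. Section 1.5.1 sets 100 imputations. Section 1.3 lists 17 main centres.
- **Sparse centres.** Section 1.5.6 avoids meta-analysis for pairs of ADNEX outcome categories because events will be few in several centres. Section 1.5.7 falls back on a pooled analysis when numbers per centre are too small, but only for subgroup c-statistics and calibration curves. Neither provision reaches the main analysis in 1.5.3.

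**The concern.** A two-stage meta-analysis needs a usable estimate and a usable variance from every centre. A proportion observed at its boundary supplies neither without a further convention. On its natural scale the usual variance is zero, so the centre with the least information can receive the most weight. On the logit scale the estimate is infinite. Because the scale is named for AUC in the paragraph before and not here, the literal reading is untransformed, but the text does not settle it.

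The gap lies on the primary path. Sensitivity at cut-offs of 1% to 5% is where values near 100% are expected. At stake are pooled sensitivities drawn towards 100% with intervals that are too narrow, a model that does not fit, or a repair chosen after the data have been seen.

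**Working it through.** The plan gives no figure on this point, so there is none to reproduce. It also gives no malignancies per centre, so every centre count below is an assumption. The pooling checks use a univariate inverse-variance model as a simplification of the bivariate one.

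**1. How often a centre shows 100%.** With n malignancies and true sensitivity p, the probability is p^n.

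| True p | n = 5 | n = 10 | n = 20 | n = 40 |
|---|---|---|---|---|
| 0.90 | 0.59 | 0.35 | 0.12 | 0.015 |
| 0.95 | 0.77 | 0.60 | 0.36 | 0.13 |
| 0.98 | 0.90 | 0.82 | 0.67 | 0.45 |

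**2. Variance after Rubin's Rules, untransformed.** In each dataset W = s(1−s)/n, which is 0 at s = 1. The total is T = (mean W) + (1 + 1/100)B, where B is the between-imputation variance. T is 0 only if the centre is at 100% in all 100 imputations. Take 5 observed malignancies, all detected, and one further imputed malignancy that is missed in k of the 100 datasets:

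- k = 1: T = 0.00023 + 1.01 × 0.00028 = 0.0005
- k = 5: T = 0.00116 + 1.01 × 0.00133 = 0.0025
- k = 20: T = 0.00463 + 1.01 × 0.00449 = 0.0092

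For comparison, 5 malignancies at sensitivity 0.90 give 0.9 × 0.1/5 = 0.018.

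**3. Effect on the pooled value.** Assumed layout: 17 centres, three of them at 100% on 5, 8 and 10 malignancies; eight with 60 malignancies at 0.92; six with 120 at 0.88. The total is 23 + 480 + 720 = 1,223, so the three small centres hold 23/1,223 = 2% of the malignancies. Weights are 1/(variance + τ²). The large centres have variances 0.92 × 0.08/60 = 0.00123 and 0.88 × 0.12/120 = 0.00088. In every column the three small centres keep an estimate of 1.00; only their variance changes.

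| τ² | Zero variance | T = 0.0005 | T = 0.0025 | Realistic, 0.09/n |
|---|---|---|---|---|
| 0.0005 | 0.940 (40% of weight) | 0.926 (25%) | 0.911 (10%) | 0.903 (3%) |
| 0.002 | 0.926 (25%) | 0.922 (21%) | 0.914 (13%) | 0.906 (5%) |
| 0.01 | 0.921 (19%) | 0.921 (18%) | 0.918 (16%) | 0.912 (10%) |

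At τ² = 0.0005 the standard error, 1/√(sum of weights), is 1/√14,981 = 0.0082 with zero variances and 1/√9,226 = 0.0104 with realistic ones.

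**4. Degenerate fits.** When two or more centres sit at exactly 100% with zero variance, the REML likelihood is unbounded as τ² approaches 0. A second assumed layout (17 centres with 3 to 150 malignancies, 633 in total) was simulated 400 times per scenario without between-imputation variance, which is the worst case. The pooled value collapsed to 1.00 in 56% of runs at true sensitivity 0.90 without heterogeneity. It did so in 99% and 100% of runs at centre medians of 0.95 and 0.98 (logit SD 0.5).

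**5. Logit reading.** logit(1) is infinite, and a mean over 100 datasets that includes one infinite value is infinite. Adding 0.5 to the affected centres makes it finite but not unbiased: in the second layout at centre median 0.98 it gave 0.962, against a crude 0.977.

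**6. AUC.** logit(AUC) is infinite at AUC = 1, and AUC is undefined without a malignancy. For an assumed AUC of 0.92 and 10% malignant, simulated centres reach AUC = 1 in about 20% of cases with 30 women, 7% with 50 and 0.3% with 100. With 30 women the chance of no malignancy is 0.9^30 = 4.2%.

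**The case against.** A reader might infer that the SAP pools on the raw scale and is therefore wrong as written. It does not say so: no scale is stated, and the same unqualified model name is used for imputed and non-imputed data. A logit inside the model is not excluded. This objection stands, and the point is therefore one of missing specification.

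A reader might also infer that any centre at 100% has zero variance. On the imputed path that holds only if all 100 datasets agree, and between-imputation variance can remove much of the distortion (step 2 and the T = 0.0025 column of step 3). Agreement is nevertheless plausible for models without CA125, whose predictions do not change between imputations. Section 1.5.1 also expects women with short conservative follow-up to be mostly benign, so few malignancies would be added.

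Comparing the pooled value with the crude proportion (1,098.2/1,223 = 0.898) would overstate the effect, because a random-effects mean moves towards the equal-weight centre mean (0.920 here) even with sound variances. The fair comparator is the same model with realistic variances.

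The counts are assumed, and the main centres were chosen for good follow-up and surgery data, so very small ones may be few. That limits any claim about size. It does not supply the missing rule.

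Finally, Rubin's Rules could be applied untransformed and the logit taken afterwards. The estimate is then finite unless all 100 datasets are at 100%. But the k = 5 case (mean 0.9917) would have logit variance 0.0025/(0.9917 × 0.0083)² ≈ 37, against 1/(5 × 0.9 × 0.1) = 2.2 for 5 malignancies at 0.90. The centre would nearly drop out, so the unstated choice decides whether it dominates or disappears.

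**Conclusion.** The concern holds as a gap in the primary analysis. Section 1.5.3 gives a two-stage procedure for imputed sensitivity and specificity without a scale or a boundary rule. Neither the untransformed nor the logit reading handles a centre at 100%, and such centres are likely at the lowest cut-offs.

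Under the assumed layout and τ² from 0.0005 to 0.002, literal untransformed pooling with zero variances raises pooled sensitivity by 0.020 (0.926 against 0.906) to 0.037 (0.940 against 0.903). With T = 0.0025 the excess is about 0.008. At τ² = 0.01 with zero variances it is 0.009 (0.921 against 0.912). These sizes rest on invented centre counts, chosen values of τ² and a univariate simplification.

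Specificity is less exposed if benign masses are numerous in each centre. The non-imputed path, as described, has no variance step and is not affected in this form. The missing AUC rule is a secondary matter, relevant only if some main centres are small or have few malignancies.

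**What to change.** Replace the imputed-data step in section 1.5.3. In each of the 100 completed datasets, fit a bivariate random-effects logistic model with a binomial likelihood to the centre 2×2 counts. Then pool the overall logit sensitivity and specificity, with their covariance matrix, across datasets by Rubin's rules and back-transform. Centres at 0% or 100% need no correction, and a centre without a malignancy still contributes to specificity. Section 1.5.4 already works in this order for calibration curves. Stating a logit scale with a zero-cell rule would also close the gap, but the 0.5 correction carries the bias shown above.

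For AUC, extend the small-numbers rule of section 1.5.7 to the main analysis: merge centres with too few malignancies into one stratum before the meta-analysis, with the minimum number stated in advance.

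The cost is SAP wording and 100 fits per model and cut-off. For four risk models at ten cut-offs, RMI at four, Simple Rules and subjective assessment, that is (4 × 10 + 4 + 1 + 1) × 100 = 4,600 fits. No new data are needed.
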